## **11.6 Handling of Missing Data**

Safety data will not be imputed.

PTE data will not be imputed.

Missing efficacy data will be imputed for the ITT analysis population. For missing data caused by worsening of scleroderma (either hand or systemic manifestation), the missing value will be replaced by the least favorable observation from the prior Visits excluding baseline. For other missing data, last observation carried forward will be the primary method of imputation. As a sensitivity analysis, multiple impute ion methods (SAS PROC MI and PROC MIANALIZE) will be used.

For the analysis of quality of life, missing responses to individual questionnaire items will be imputed using the methods prescribed by the questionnaire vendor.

## **11.7 Protocol Deviations**

Deviations from the protocol including violations of inclusion/exclusion criteria will be assessed as “minor” or “major” in cooperation with the Sponsor. Deviations will be defined prior to un-blinding. Major deviations may result in removal from the PTE analysis population.

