## Summary of Changes Document – Clinical Protocol

---

In November 2015 the STYLE Clinical Trial Protocol—Rev A, August 21, 2015 was modified to Rev B, November 24, 2015. This document highlights the changes that were made in the revision.

1. **Blinding (Section 5.3):** we adjusted the document to accurately reflect which parties are blinded and unblinded in carrying out the protocol. Given that a no-fat control is currently a group within the study and it is unfeasible to disguise this treatment relative to a fat containing arm, the sponsor, data management personnel (CRO), and study monitors will be aware of which treatment the subject received. It is imperative to note that the above parties have no potential impact in either the outcome or risk profile as core analysis (e.g., global and macrophotography) will remain conducted by blinded observers. It should also be noted that the statistician working to analyze the data will also remain blinded.
2. **Questionnaires (Sections 8, 9.6, & Appendix A):** we adjusted the protocol to remove inconsistencies with the timing of both investigator and subject questionnaires. Both of these questionnaires (attached in the correspondence) are not relevant for any pre-procedure assessment as they reflect perceived changes subsequent to the intervention. As such, the sections of the document reflecting this timing have been amended accordingly. This change has no potential impact in either the outcome assessment or risk profile of the protocol.
3. **Timing of visit (Sections 9.1 & Appendix A):** the original protocol called for acquisition of both global and macrophotography at Day -1. In the course of working with the approved vendor (Canfield Scientific), it became evident that this time period would not allow adequate time to monitor for the quality of the images obtained. As such, we are proposing that both global and macro photography is acquired at least one month and no later than one week prior to the scheduled intervention to allow for this critical quality assessment. With this change, we are eliminating one round of global photography. This change has no potential impact in either the outcome assessment or risk profile of the protocol.

Subcutaneous Transplantation of Autologous Cell Enriched Adipose  
Tissue For Follicular Niche Stimulation in EarLY Stage ALopecia  
Androgenetica (STYLE): a Randomized, Blinded, Controlled Trial

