### **5.3 Blinding Procedures and Safeguards**

The following will be the “blinded parties”, meaning that the listed will have no knowledge of the patient’s treatment assignment:

- Patients
- Core Laboratories
- Data Management personnel
- Sponsor
- Study Monitors

The “**unblinded parties**”, meaning those that will or may have knowledge of a patient’s treatment assignment, will be the following:-

- Investigators
- Unblinded Pharmacist or designee involved in the dose preparation procedures and randomization of the patient
- Data Monitoring Committee Members
- Unblinded Statistician

The study blind should not be broken except in a medical emergency (where knowledge of the test material received would affect the treatment of the emergency) or regulatory requirement (e.g., for SAEs or death).

If unblinding becomes necessary, the Investigator should notify the Sponsor or the Medical Monitor as soon as possible. If the blind is broken, the date, time and reason must be recorded in the Subject’s electronic case report form (eCRF), together with a note of a protocol violation if applicable, and any applicable reports [e.g. Adverse Event (AE)].

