### **5.3 Blinding Procedures and Safeguards**

The following will be the “blinded parties”, meaning that the listed will have no knowledge of the patient’s treatment assignment:

- Patients
- Core Laboratories
- Statistician

The “**unblinded parties**”, meaning those that will or may have knowledge of a patient’s treatment assignment, will be the following:-

- Investigators
- Unblinded Pharmacist or designee involved in the dose preparation procedures and randomization of the patient
- Data Monitoring Committee Members

The study blind should not be broken except in a medical emergency (where knowledge of the test material received would affect the treatment of the emergency) or regulatory requirement (e.g., for SAEs or death).

If unblinding becomes necessary, the Investigator should notify the Sponsor or the Medical Monitor as soon as possible. If the blind is broken, the date, time and reason must be recorded in the Subject’s electronic case report form (eCRF), together with a note of a protocol violation if applicable, and any applicable reports [e.g. Adverse Event (AE)].

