## **11.5 Subject Disposition & Analysis Populations**

Reasons for withdrawal post-randomization will be summarized.

The treatment analyses will be performed on intent-to-treat basis as well as on a per-treatment-evaluable basis, as defined below:

Safety: All treated subjects; subjects will be analyzed as treated.

Intent-to-Treat (ITT): All randomized subjects; randomization will occur on procedure day prior to liposuction. Subjects will be included in the analysis as randomized

Per-Treatment-Evaluable (PTE): All randomized subjects who have received treatment and follow-up information is available. Protocol violators, where the violation is judged to affect the interpretation of the treatment effect will be excluded. All exclusions will be made prior to the breaking of the treatment blind.

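### The rule that PTE exclusions precede unblinding does not bind the Sponsor, the only party named in grading deviations, because Rev B no longer blinds it

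*Combined protocol and SAP*

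**What the plan says.** **Grading and exclusion (Rev B).** Section 11.7 has deviations graded minor or major "in cooperation with the Sponsor. Deviations will be defined prior to un-blinding". It names no other participant in the grading. The consequence is discretionary: "Major deviations may result in removal from the PTE analysis population". Section 11.5 adds a judgement standard without saying who judges: "Protocol violators, where the violation is judged to affect the interpretation of the treatment effect will be excluded". The safeguard offered is timing: "All exclusions will be made prior to the breaking of the treatment blind".

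**Who is blinded (Rev B).** Section 5.3 gives a list, "meaning that the listed will have no knowledge of the patient’s treatment assignment", with three entries: patients, core laboratories and the statistician. Investigators, the dose-preparing pharmacist or designee, and the DMC are listed as unblinded. The Sponsor, data management and monitors are on neither list. The Summary of Changes, item 1, settles their status. It names the sponsor and the CRO's data managers and adds that "study monitors will be aware of which treatment the subject received".

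**Role of the PTE set.** Section 11 makes ITT the primary efficacy population and PTE supportive of it. Section 11.6 imputes missing efficacy data for ITT and does not impute for PTE.

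**The concern.** A rule that exclusions come before unblinding protects an analysis set only if the people deciding are still blind when they decide. Under Rev B the Sponsor takes part in the grading and is not blind. The criteria also leave room for judgement: whether a violation affects interpretation, and whether a major deviation leads to removal.

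At stake is what agreement between PTE and ITT is worth. A reader will take a concordant PTE result as reassurance, all the more because PTE avoids the last-observation-carried-forward imputation used for ITT. If membership can be settled with arm known, that reassurance weakens. With 20 subjects in each of the three larger arms, a few exclusions can move a mean.

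**Working it through.** The protocol gives no figure to reproduce here, and section 11.2 says the sample size does not come from a power calculation. The main check is textual. A simulation then gauges the size.

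**1. The two revisions side by side**

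| Item | Rev A | Rev B |
|---|---|---|
| Blinded parties (5.3) | Patients, core laboratories, "Data Management personnel", Sponsor, study monitors | Patients, core laboratories, statistician |
| Grading of deviations (11.7) | With the Sponsor, before unblinding | Same wording |
| PTE exclusions (11.5) | Before the blind is broken | Same wording |

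In Rev A the Sponsor was blinded, so the rule was coherent. Rev B changed 5.3 and left 11.5 and 11.7 as they were. The point does not rest on a mismatch between the change log and the current text: Rev B 5.3 and the Summary of Changes agree.

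**2. Does the stated defence cover this?** The Summary of Changes says that "the above parties have no potential impact in either the outcome or risk profile", and supports this with blinded image analysis and a blinded statistician. Neither has a stated part in deciding PTE membership. A blinded statistician who analyses a set shaped by unblinded people inherits their choices.

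**3. Illustrative size.** Inputs from the protocol: 20 subjects per larger arm (5.2; 70 × 2/7 = 20) and two-sided 0.05 (11.1). Assumptions: standard normal outcome, no true effect, unadjusted t-test of one active arm v fat-alone control, *m* of the 20 active subjects having a deviation unrelated to outcome, and the *k* worst of those *m* removed. The documents give no deviation count, so *m* is varied.

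Expected shift in the active mean, in SD units: minus the sum of the expected values of the *k* lowest of *m* standard normal values, divided by (20 − *k*).

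- *m* = 3, *k* = 2: (0.846 + 0.000)/18 = 0.05
- *m* = 4, *k* = 2: (1.029 + 0.297)/18 = 0.07
- *m* = 5, *k* = 2: (1.163 + 0.495)/18 = 0.09
- *m* = 20, *k* = 1: 1.867/19 = 0.10
- *m* = 20, *k* = 2: (1.867 + 1.408)/18 = 0.18

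Simulated two-sided type I error (400,000 runs each):

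| Excludable subjects *m* | Removed *k* | Shift (SD) | Type I error |
|---|---|---|---|
| none | 0 | 0 | 5.0% |
| 3 | 2 | 0.05 | 5.0% |
| 4 | 2 | 0.07 | 5.4% |
| 5 | 2 | 0.09 | 5.8% |
| 20 | 1 | 0.10 | 6.8% |
| 20 | 2 | 0.18 | 10.0% |

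Runs with fewer repetitions differ by about 0.1 percentage point (for example 5.1% to 5.9% for *m* = 3 to 5, and 10.1% in the last row). The last two rows need every subject to be excludable. All rows with removals also need the outcome to be known when the exclusion is made.

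**The case against.** **A blind remains.** Patients, core laboratories and the statistician are still blinded, so fixing exclusions before the statistician is unblinded has some value. Section 11.7 also speaks of cooperation with the Sponsor, not a decision by the Sponsor alone. This stands: it would be too strong to infer that the safeguard has vanished. It still does not bind the one party named.

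**Timing of the Sponsor's knowledge.** A reader might infer that the Sponsor knows each assignment from Day 1, since randomization occurs on the procedure day. The documents do not say so. The Summary of Changes says the Sponsor will be aware, without saying when.

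**Arm and outcome are both needed.** No section says the Sponsor sees efficacy values by arm before PTE is fixed. That is correct. Equally, no section prevents it: Sponsor representatives compare eCRFs with medical records (14.3.3) and data management is run by the Sponsor or a designee (14.3.5).

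**The 10% figure overstates the risk.** Section 11.5 allows removal only of violators whose violation affects interpretation, not of any poor responder. This stands, and it is why the restricted rows are the better guide. The planned analysis is also ANCOVA with Dunnett comparisons. Using Dunnett with two active arms and no covariate, even the unrestricted drop-2 case gives about 8.3% familywise.

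**Little depends on PTE, and the SAP may help.** PTE is supportive, the primary endpoint is safety without testing, and section 11.1 promises a separate SAP that could list major deviations. The limited reach is accepted. Because that SAP is not part of the text reviewed, the absence of such a list cannot be held against the plan. The conflict between 5.3 and 11.5/11.7 is in the protocol itself and would still need resolving.

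**Conclusion.** The point holds in a limited form. Sections 11.5 and 11.7 protect PTE membership by timing relative to unblinding, and Rev B removed that protection for the only party named in the grading. This is a stated rule that no longer works as written, not just missing detail.

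The reach is the supportive PTE analysis of the secondary efficacy endpoints. ITT keeps all randomized subjects as randomized, and the safety population is all treated subjects, so neither is affected. The documents show an opening for selective exclusion. They do not show that it happened, and a reader should not infer that.

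The size depends on assumptions: with 3 to 5 deviators in one arm and the worst 2 removed, inflation is from nothing measurable to under 1 percentage point. About 10% is an upper bound, not an expected value. The change is worth making because it is cheap and restores the meaning of the PTE comparison, not because a large error has been demonstrated.

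**What to change.** - **Criteria.** Set objective major-deviation criteria in the SAP, state which of them remove a subject from PTE, and refer to them in 11.5 and 11.7.
- **Decision.** Have the blinded statistician decide and sign PTE membership before database lock, from listings without arm or efficacy values.
- **Deviations that reveal the arm.** Cell count and viability criteria apply to ADRC preparation (7.1.1), and a negative Gram stain is not required for the no-fat arm (7.3). Showing such deviations to the statistician could break the blind that Rev B keeps. Classify them in advance by rule and pass on only a masked major/minor code, without the type of deviation.
- **Sponsor's role.** Limit it in 11.7 to supplying facts.
- **Wording.** State in 11.5 and 11.7 whose blind is meant, and list the Sponsor, data management and monitors as unblinded in 5.3.

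The cost is protocol and SAP wording, some masked coding work, and less room for case-by-case clinical judgement. If clinical judgement is wanted for borderline deviations, a blinded clinical reviewer would be a small added cost. Visits, treatment and sample size do not change.

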## **11.8 Data Monitoring Committee**

The independent Data Monitoring Committee (DMC) will be comprised of medical specialists and a biostatistician who are not participants in the study. The DMC will be provided with all safety data as well as efficacy data for the primary and secondary endpoints in order to fully

evaluate the benefit to risk profile of the study procedures. The DMC will be responsible for the review of the data and generate recommendations on the conduct of the trial.

The DMC will be asked to review data and generate recommendations after 10, 20 and 40 subjects have at least 1 week of follow-up.

### ***11.8.1 Adverse Events Initiating Safety Review***

The Sponsor is to be informed of the following adverse events within 24 hours of the site becoming aware of the event:

- Gangrene of the scalp in two (2) or more within fourteen (14) days of the procedure
- Infection of the scalp requiring hospitalization and intravenous antibiotics in two (2) or more patients within seven (7) days of the procedure

Within 24 hours of notification, the Sponsor will report the event to the DMC Chair for evaluation. The DMC Chair will review the event and decide whether to convene a meeting of the DMC.

In all cases, the DMC Chair or the DMC will be responsible for recommendations to continue the trial, continue the trial with modifications, pause the trial such that further evaluation can be conducted, or terminate the trial.

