### 7.3 Study Treatment Pre-Injection Sterility Testing

[figure not shown]
Following cell processing in the Celution System, sterility testing will be performed as described below and more fully in the *Study Reference Manual*.

A negative Gram stain test result is required prior to injection of ADRCs and/or fat alone control. A negative Gram stain test result is not required prior to injection of saline in the no-fat control arm. If the sample is determined to be positive for bacteria then the cellular administration procedure must be stopped and the subject should not receive any study treatment.

Further testing (BacT Alert Culture and Sensitivity) will be performed in order to test for the presence of any low level microbial contamination that might not be apparent in the gram stain test. Should a culture be deemed positive for microbial activity, the investigator will be immediately notified. The study patient will be evaluated and a course of treatment and/or antibiotics may be administered, as determined by the study investigator. The source of the contamination will be evaluated as appropriate. The FDA and IRB will be notified within 15 days of the investigator being made aware of any positive test results.

The following flow chart describes the activities associated with positive or negative outcomes in these two tests of sample sterility.

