## **12 ADVERSE EVENTS / SERIOUS ADVERSE EVENTS**

### **12.1 Definitions**

An **adverse event (AE)** is defined as any undesirable experience occurring to a Subject during the course of the study, whether or not it is related to the test material or the study procedure. Expected adverse events are those that are listed as known risks of the liposuction or injection procedure including those described in this protocol, informed consent, and/or the Investigator's Brochure.

A **serious adverse event (SAE)** is defined as any untoward medical occurrence that:

- Results in death,
- Is life-threatening,
- Requires or prolongs Subject hospitalization
- Results in persistent or significant disability or incapacity
- Is an important medical event(s) that may not be immediately life-threatening or result in death or hospitalization but that may jeopardize the Subject or require intervention to prevent one of the above outcomes
- Is a congenital anomaly/birth defect.

Medical and scientific judgment should be exercised in deciding whether a case is serious and whether expedited reporting is appropriate.

An **Unanticipated Adverse Device Effect** is defined as any serious adverse effect on the health and safety or any life-threatening problem or death caused by, or associated with the Celution or Puregraft system devices, if that effect, problem, or death was not previously identified in nature, severity, or degree of incidence in the investigational plan or application or any other unanticipated serious problem with the Celution or Puregraft system devices that relates to the rights, safety or welfare of subjects.

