## **12.2 Procedures for AE Reporting**

All AEs will be recorded by the investigator or designee on the appropriate electronic case report form (eCRF). Events that occur prior to the liposuction-related activities, including those that are considered serious, are to be recorded in the medical history. Events, including SAEs, which occur after liposuction-related activities are initiated on procedure day, are to be recorded on the AE eCRF. The investigator will evaluate the relationship of the adverse event to both the test material and study procedure as unrelated, unlikely, possibly, probably, or definitely related and will record the findings, including all pertinent details of the event on the eCRF.

In addition, the Investigator or designee will report any serious adverse events, including UADE, occurring during this study to the Sponsor and Medical Monitor as soon as possible, but no later than 24 hours after the Investigator first identifies the adverse event.

The Investigator will take appropriate measures to ensure the subject's well-being and document these measures on the appropriate eCRF.

All serious adverse events experienced will be monitored until the event has resolved, any abnormal laboratory values have returned to baseline or stabilized at a level acceptable to the Investigator and Medical Monitor, or until there is a satisfactory explanation for the changes observed.

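### Expedited DMC notice of clustered serious scalp infection stops 7 days after the procedure, leaves the qualifying date undefined, and has no scheduled DMC review behind it after 40 of 70 subjects

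*Combined protocol and SAP*

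**What the plan says.** Section 11.8.1 lists two events that start an expedited safety review. The one on serious infection reads: "Infection of the scalp requiring hospitalization and intravenous antibiotics in two (2) or more patients within seven (7) days of the procedure". The other has a window twice as long: "Gangrene of the scalp in two (2) or more within fourteen (14) days of the procedure".

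The site informs the Sponsor within 24 hours of becoming aware. Then: "Within 24 hours of notification, the Sponsor will report the event to the DMC Chair for evaluation". The Chair decides whether to convene the committee. Both windows run from the procedure. Neither bullet says whether onset, diagnosis, admission or start of IV treatment must fall inside, and no reason is given for the different lengths.

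Section 11.8 sets the routine oversight: "The DMC will be provided with all safety data", with reviews "after 10, 20 and 40 subjects have at least 1 week of follow-up". Section 4.2 sets the sample size at 70. No review is scheduled after the one at 40 subjects.

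Two other routes carry infection information, and neither names the DMC. A hospitalized case meets the SAE definition in Section 12.1 ("Requires or prolongs Subject hospitalization"), and under Section 12.2 the investigator must, within 24 hours, "report any serious adverse events, including UADE, occurring during this study to the Sponsor and Medical Monitor". For product cultures, Section 7.3 requires immediate notice to the investigator and adds: "The FDA and IRB will be notified within 15 days of the investigator being made aware of any positive test results".

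Rev A reads the same on the two triggers and the review schedule.

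**The concern.** The trial injects freshly processed autologous tissue into the scalp. Section 10.1.1 lists infection as a delivery risk, and Section 7.3 accepts that low-level contamination can escape the Gram stain. In Appendix A the first follow-up visit is at Week 1 (± 1 day) and the next at Week 6, so the infection window closes at about the first planned check. A pair of serious infections appearing in the second week would not meet the trigger, although a pair of gangrene cases on the same days would.

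The undefined date adds a second problem. A patient with onset on day 5 and admission on day 8 counts on one reading and not on another, so sites could apply the rule differently.

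What is at stake is independent oversight while subjects are still being treated. Once the 40-subject review has passed, a Sponsor that follows the text to the letter may leave the DMC unaware of a cluster.

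**Working it through.** **Routes for two or more hospitalized scalp infections treated with IV antibiotics**

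| When the cluster arises | Required 24-hour notice to DMC Chair | Scheduled DMC review to follow |
|---|---|---|
| Within 7 days of the procedure, any point in the trial | Yes (11.8.1) | Only if before the 40-subject review |
| After day 7, before the 40-subject review | No | Yes (11.8) |
| After day 7, after the 40-subject review | No | None |

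A case that progresses to scalp gangrene within 14 days counts toward the other trigger. The third row is the gap. Subjects beyond the last review count: 70 − 40 = 30.

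**How much follow-up lies past the last review.** Section 4.4 gives about 6 months of enrolment. Assuming uniform accrual, the third review falls at about day 111, with about 42 subjects enrolled and 37 past day 14. About 55% of all day 8–14 follow-up and 18% of all day 8–168 follow-up precede it (12% and 27% of the latter with 4- and 9-month accrual).

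**Chance that the 7-day trigger misses a cluster.** The plan states no operating characteristic for the trigger, so there is no figure to reproduce. Two inputs are assumed: r, the rate per subject (1% or 2%), and p, the share of onsets within 7 days (50%, 70% or 90%).

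*Last 30 subjects only:*

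miss = P(Bin(30, r) ≥ 2) − P(Bin(30, r·p) ≥ 2)

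For r = 1%, P(≥ 2) = 1 − 0.99^30 − 30 × 0.01 × 0.99^29 = 1 − 0.7397 − 0.2242 = 0.0361. With p = 50% the in-window rate is 0.5%, and the same formula gives 0.0099. The difference is 0.0262.

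*Allowing one earlier case:* at most one case in the first 40, two or more in total, and fewer than two inside 7 days, by exact calculation. The chance of such a cluster, caught or not, is P(0 of 40) × P(≥ 2 of 30) + P(1 of 40) × P(≥ 1 of 30). For r = 1% this is 0.669 × 0.0361 + 0.270 × 0.260 = 0.0945; for r = 2% it is 0.219.

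| r | p | P(≥ 2 of 30) | Of which trigger met | Missed, last 30 only | Missed, allowing one earlier case |
|---|---|---|---|---|---|
| 1% | 50% | 3.6% | 1.0% | 2.6% | 6.8% |
| 1% | 70% | 3.6% | 1.9% | 1.7% | 4.5% |
| 1% | 90% | 3.6% | 3.0% | 0.6% | 1.6% |
| 2% | 50% | 12.0% | 3.6% | 8.4% | 14.9% |
| 2% | 70% | 12.0% | 6.6% | 5.5% | 9.5% |
| 2% | 90% | 12.0% | 10.1% | 1.9% | 3.3% |

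The last-30 column is a lower bound, because it ignores pairs with one earlier case. The final column still leaves out two cases among the first 40 whose onsets both follow the last review.

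**What a 14-day window would recover.** The misses above count every onset after day 7. If a quarter to a half of those late onsets fall in days 8–14 (a further assumption), the one-earlier-case calculation repeated with p + s(1 − p) in place of p, for s = 0.25 to 0.5, recovers about 0.4 to 3 percentage points at r = 1% and 0.8 to 7 points at r = 2%.

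**The case against.** The strongest reply has four parts.

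First, a reader might infer that a late infection cluster need never reach the DMC. The documents do not support that. Section 11.8 gives the committee all safety data without a time limit and fixes three reviews, so a day-8 or later cluster arising before the 40-subject review must be seen there. What is missing is urgency before that review, and both urgency and a set date after it. This correction stands in full.

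Second, a reader might take the 7-against-14 mismatch for a mistake. Gangrene and infection are different events, a clinical reason for different windows may exist, and nothing in the documents shows that 7 days is wrong for infection. This also stands: the case for change rests on the missing back-up, not on the mismatch.

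Third, safeguards exist. Each case reaches the Sponsor and Medical Monitor within 24 hours, cultures are reported, a negative Gram stain precedes ADRC and fat-alone injections, and nothing stops the Sponsor from referring a cluster. Section 10.1.5 lists infection after liposuction as rare. Harm therefore needs two serious late infections and a Sponsor, already informed of both, that does not refer them. That limits the severity. It does not supply a required route, because none of these safeguards names the DMC.

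Fourth, widening the window neither adds a review after 40 subjects nor sends SAEs to the DMC, so it treats only part of the problem. That is correct, and the date ambiguity matters only in borderline cases. Neither point is a reason to refuse a change that costs almost nothing.

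**Conclusion.** The point holds in a limited form. No text requires expedited DMC notice of a serious infection cluster with onset after day 7. Once the 40-subject review has passed, no date is set for such a cluster to reach the DMC, and it depends on Sponsor referral after SAE reporting. It is not established that the 7-day window is an error, or that late clusters bypass the DMC throughout the trial.

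Under the assumed rates and onset shares, a missed cluster has probability 0.6% to 2.6% at a 1% rate and 1.9% to 8.4% at 2%, counting only the last 30 subjects. Allowing one earlier case, the ranges are 1.6% to 6.8% and 3.3% to 14.9%. Both inputs are illustrative. The figures give the chance that the 7-day trigger misses a cluster, not the benefit of a 14-day window, which is smaller. I would call this a cheap, worthwhile improvement, between optional and recommended.

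**What to change.** In Section 11.8.1, extend the infection window from 7 days to at least the 14 already used for gangrene, and state that the date of onset counts for both triggers, even if admission or IV treatment comes later. Keep the case definition, the two-patient count and the 24-hour route.

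The cost is a wording amendment and an occasional extra notice to the DMC Chair, who still decides whether to convene. Onsets after day 14 would remain uncovered. Covering them would take a larger change, such as a scheduled review after 40 subjects or direct routing of these SAEs to the DMC.
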